2.	The patient is either scheduled to receive, receiving, or is anticipated to require any chemotherapy for prostate cancer, or any other cancer, during the period of his participation in the study.
3.	The patient is either scheduled to receive, or anticipated to require any surgical intervention for their prostate cancer during the period of his study participation.
4.	The patient has any condition that in the opinion of the Investigator may preclude the administration of subcutaneous Decapeptyl SR injections.
5.	The patient has received treatment with any LHRHa within 1 year prior to study entry.
6.	The patient has a history of hypersensitivity to Decapeptyl SR or CPA or to any of the excipients of Decapeptyl SR or CPA.
7.	The patient has any contraindication to treatment with anti- androgens, including, but not limited to clinically significant abnormalities in liver function.
8.	The patient has been treated with oestrogens or steroid androgens within the 12 months prior to screening, or is receiving treatment with non-steroid anti-androgens at the time of the Screening visit.
9.	The patient, in the opinion of the Investigator is at risk of serious complications in the event of tumour flare (e.g. vertebral metastases threatening spinal cord compression, significant obstructive

r	
	uropathy) on initiation of Decapeptyl SR treatment, despite concomitant treatment with anti-androgens.
	10. The patient has any other condition that, in the opinion of the Investigator, might increase the risk to the patient or decrease the chance of obtaining satisfactory data needed to achieve the objective(s) of the study.
	11. The patient is likely to require treatment during the study with drugs that are not permitted by the study protocol (For a list of drugs not permitted see Appendix 2).
	12. The patient has received any investigational drug, within 30 days prior to the study or is scheduled to receive such a drug during the study.
	13. The patient has a history of, or known current, problems with alcohol abuse.
	14. The patient has any mental condition rendering him unable to understand the nature, scope and possible consequences of the study.
	15. The patient has previously been enrolled in this study.
Study Treatment:	Study Product: Decapeptyl SR (triptorelin acetate)

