	Decapeptyl SR (triptorelin acetate) is a micro-particle, sustained release LHRHa that is licensed for the treatment of advanced prostate cancer in the UK. The doses/formulations to be used in this study are within the constraints of the UK product licence:
	• Decapeptyl SR 3 mg (1-Month formulation).
	• Decapeptyl SR 11.25 mg (3-Month formulation).
	These formulations are already licensed in the UK for administration by intramuscular injection. Triptorelin (Gonapeptyl 3mg) is licensed for SC and IM administration.
	The treatment regimen in this study is consistent with the recommended treatment for prostate cancer in this patient population, as documented in the Summary of Product Characteristics (SPC) for Decapeptyl SR (see Appendix 3).
	The investigational product will not be used for purposes other than as defined in this protocol. Administration of the study drug will be performed by the Investigator, or study staff to whom this task has been delegated by the Investigator.
	Concomitant medication: Cyproterone Acetate 100mg three times daily, from Baseline Visit to Day 14.
Study Evaluations:	Primary Efficacy Variables:
	The proportion of patients with STT $\leq 50 \text{ ng/dL 4}$ months after their first injection of Decapeptyl SR.
	Secondary Efficacy Variables:
	Proportion of patients with STT \leq 50 ng/dL 1 month after their first

	injection of Decapeptyl SR.
	Proportion of patients with STT \leq 50 ng/dL 1 month and 3 months after the second injection of Decapeptyl SR.
	Plasma triptorelin levels at all assessment time-points.
	STT and PSA levels at all assessment time-points.
	Safety Variables:
	1. Safety of subcutaneous route of administration will be assessed by examining the incidence of adverse events (AEs) and changes in concomitant medications at each assessment time-point.
	2. Tolerability of the subcutaneous route of injection will be assessed by observation of the injection site and by means of a phone call 24 hours after each injection. Patients will provide feedback on the following parameters.
	• Pain (severity, time of onset in relation to the injection, duration).
	• Redness (severity, time of onset in relation to the injection, duration).
	• Swelling (severity, time of onset in relation to the injection, duration).
	Severity of injection site reactions will be graded using a 4 point scale (none, mild, moderate and severe).

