4. SELECTION & WITHDRAWAL OF SUBJECTS

4.1 Patient Selection Criteria

4.1.1 Inclusion criteria

Patients must satisfy all of the following entry criteria before they will be allowed to participate in the study:

- 1. The patient must give written (personally signed and dated) informed consent before starting any study-related procedure, which means any assessment or evaluation that would not have formed part of their normal medical care.
- 2. The patient is male and is 18 years of age or older.
- 3. The patient has a histologically or cytologically confirmed diagnosis of prostate cancer and meets the following criteria:
 - Stage T3 or T4, N (*any*), M (*any*) (see Appendix 1) with a PSA >5ng/ml or
 - Biochemical relapse following radical prostatectomy or radical radiotherapy for prostate cancer
- 4. Medical castration by means of LHRHa therapy is indicated for the patient.
- 5. The patient has a life expectancy of at least 12 months.
- 6. The patient is able and willing to comply with the requirements of the protocol.

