4.1.2 Exclusion Criteria

Patients who satisfy any of the following criteria must not be included in the study:

- 1. The patient has undergone bilateral orchidectomy.
- 2. The patient is either scheduled to receive, receiving or anticipated to require any chemotherapy for prostate cancer or any other cancer during the period of his participation in the study.
- 3. The patient is either scheduled to receive, or anticipated to require any surgical intervention for their prostate cancer during the period of his study participation.
- 4. The patient has any condition that in the opinion of the Investigator may preclude the administration of subcutaneous Decapeptyl SR injection.
- 5. The patient has received treatment with any LHRHa within one year prior to study entry.
- 6. The patient has a history of hypersensitivity to Decapeptyl SR or CPA and any of their excipients.
- 7. The patient has any contraindication to treatment with anti-androgens, including, but not limited to clinically significant abnormalities in liver function.

- 8. The patient has been treated with oestrogens or steroid androgens within the 12 months prior to screening, or is receiving treatment with non-steroid antiandrogens at the time of the Screening visit.
- 9. The patient, in the opinion of the Investigator, is at risk of serious complications in the event of tumour flare (e.g. vertebral metastases threatening spinal cord compression, significant obstructive uropathy) on initiation of Decapeptyl SR treatment despite concomitant treatment with anti-androgens.
- 10. The patient has any other condition that, in the opinion of the Investigator, might increase the risk to the patient or decrease the chance of obtaining satisfactory data needed to achieve the objective(s) of the study.
- 11. The patient is likely to require treatment during the study with drugs that are not permitted by the study protocol (See Appendix 2).
- 12. The patient has received any investigational drug therapy within 30 days prior to study entry, or is scheduled to receive such a drug during the study period.
- 13. The patient has a history of, or known current, problems with alcohol abuse.
- 14. The patient has any mental condition rendering him unable to understand the nature, scope and possible consequences of the study.
- 15. The patient has previously been enrolled in the study

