4.3 Contraindications

Hypersensitivity of GnRH analogues or to any of the excipients.

In prostate cancer, DECAPEPTYL SR 3mg should not be prescribed in patients presenting with spinal cord compression or evidence of spinal metastases.

In endometriosis and uterine fibroid treatment, confirm that the patient is not pregnant before beginning treatment.

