4.2 Posology and method of administration

Prostate cancer

One intramuscular injection should be administered every 3 months. No dosage adjustment is necessary in the elderly.

Endometriosis

One intramuscular injection should be administered every 3 months. The treatment must be initiated in the first five days of the menstrual cycle. Treatment duration depends on the initial severity of the endometriosis and the changes observed in the clinical features (functional and anatomical) during treatment. The maximum duration of treatment should be 6 months (two injections). A second course of treatment with DECAPEPTYL SR 11.25 mg or with other GnRH analogues should not be undertaken due to concerns about bone density losses.

Precocious puberty

One intramuscular injection of Decapeptyl *SR* 11.25mg repeated every 3 months. Treatment should be stopped around the physiological age of puberty in boys and girls and should not be continued in girls with a bone maturation of more than 12 years. There are limited data available in boys relating to the optimum time to stop treatment based on bone age, however it is advised that treatment is stopped in boys with a bone maturation age of 13-14 years.

Contraindications

Hypersensitivity of GnRH analogues or to any of the excipients.

In prostate cancer, DECAPEPTYL SR 11.25 mg is contraindicated in patients presenting with spinal cord compression or evidence of spinal metastases.

In endometriosis, confirm that the patient is not pregnant before beginning treatment.

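### Exclusion 9 leaves spinal metastases to the Investigator's judgement of flare risk, although both appended SPCs contraindicate the drug whenever there is evidence of them

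*Protocol*

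**What the plan says.** Inclusion 3 (Protocol 4.1.1) admits men with "Stage T3 or T4, N (*any*), M (*any*) (see Appendix 1) with a PSA >5ng/ml", or with biochemical relapse after radical treatment. Metastatic disease is therefore eligible, wherever the metastases are.

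Exclusion 9 (4.1.2) is the only criterion that names the spine. It removes a man who, in the Investigator's opinion, "is at risk of serious complications in the event of tumour flare (e.g. vertebral metastases threatening spinal cord compression, significant obstructive uropathy"), and the risk must remain despite concomitant anti-androgens. The synopsis has the same rule: "The patient, in the opinion of the Investigator is at risk of serious complications in the event of tumour flare".

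Appendix 3 reproduces the SPCs of both study products. Under Contraindications, the 3 mg SPC (section 4.3) states that "DECAPEPTYL SR 3mg should not be prescribed in patients presenting with spinal cord compression or evidence of spinal metastases". The 11.25 mg SPC, under its Contraindications heading, states that "DECAPEPTYL SR 11.25 mg is contraindicated in patients presenting with spinal cord compression or evidence of spinal metastases".

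The synopsis (Study Treatment) says that the regimen "is consistent with the recommended treatment for prostate cancer in this patient population, as documented in the Summary of Product Characteristics (SPC").

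**The concern.** The protocol and the product information attached to it do not exclude the same men. The SPCs ask whether there is evidence of spinal metastases. Exclusion 9 asks whether the Investigator thinks that flare would cause serious complications despite anti-androgen cover. A man can meet the SPC contraindication and still pass exclusion 9.

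The harm at stake is neurological. An LHRH analogue first raises testosterone, and the 11.25 mg SPC (section 4.8) lists worsening neurological signs of vertebral metastases as common at the start of treatment. A site that applies exclusion 9 as written could enrol and dose a man whom the attached SPC says should not receive the drug. A reader of the synopsis would not learn this.

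**Working it through.** The protocol states no figure on this point, so the check compares texts.

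**1. The two rules side by side**

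| Element | SPCs, Contraindications (3 mg and 11.25 mg) | Protocol, exclusion 9 |
|---|---|---|
| Trigger | Cord compression or evidence of spinal metastases | Risk of serious flare complications; vertebral metastases that threaten the cord are an example |
| Who decides | No reference to opinion | Investigator's opinion |
| Anti-androgen cover | Not mentioned; does not lift the rule | Risk must remain despite it |

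Exclusion 9 adds three conditions that neither SPC has. Cord compression and spinal metastases judged threatening are covered. Spinal metastases judged non-threatening under CPA are not.

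**2. Does another criterion catch these men?**

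- Inclusion 4 requires that LHRH-analogue castration be indicated. It does not refer to the SPC contraindications.
- Exclusion 4: "The patient has any condition that in the opinion of the Investigator may preclude the administration of subcutaneous Decapeptyl SR injection". This again rests on opinion and does not name the spine.
- Exclusion 6 covers hypersensitivity. This is the other SPC contraindication relevant to men, and here it does not depend on opinion.
- Exclusion 7 covers any contraindication to anti-androgens, but not to Decapeptyl SR.
- Exclusion 10: "The patient has any other condition that, in the opinion of the Investigator, might increase the risk to the patient". This also rests on opinion.

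None excludes spinal metastases outright.

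**3. Do the safeguards remove the contraindication?** Section 2.2 says that an anti-androgen prevents flare, and 3.5.2 gives every patient two weeks of CPA. Neither SPC lifts its contraindication when an anti-androgen is used. Section 4.4 of both SPCs suggests considering an anti-androgen for three days before treatment, whereas the protocol starts CPA on the day of injection. After the first injection, the schedule (3.4) has a telephone call at 24 hours and then no contact until Month 1.

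**4. How many men?** The documents do not say. Section 2.1 puts bone metastases at diagnosis at about 30%, but that covers any bone and prostate cancer in general, and this trial also admits biochemical relapse. The figure shows only that the situation can arise.

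**5. Recruitment cost, as an illustration only.** Assume that a share *s* of otherwise eligible men has known spinal metastases, with *s* between 0 and 0.30 (the any-bone figure as a ceiling). The number needed to enrol 50 is 50/(1 − *s*):

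- *s* = 0: 50/1 = 50
- *s* = 0.30: 50/0.70 = 71.4, rounded up to 72

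**The case against.** The strongest reply is that the SPCs are part of the protocol, as Appendix 3. An Investigator who reads them would treat a listed contraindication as a condition that precludes the injection and would exclude the man under exclusion 4, or find inclusion 4 unmet. To dose him, the Investigator would have to pass him under inclusion 4 and exclusions 4, 9 and 10 with the SPC to hand. This makes the error less likely. It does not remove it, because these criteria are general or rest on opinion, and exclusion 9, the one that addresses vertebral metastases, implies that only threatening ones matter.

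Other points deserve weight:

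- Treatment starts with 3 mg, and the 3 mg SPC (4.8) describes flare bone pain as occasional. The 11.25 mg SPC adds that the early symptoms pass in one or two weeks. This weakens the supporting evidence on early neurological worsening, but the 3 mg SPC carries the same contraindication.
- Section 2.2 reports flare in about 5% of patients. That is a rate of flare, not the share of men with spinal metastases, and it does not measure the gap.
- Section 4.4 of both SPCs asks for careful monitoring of men at risk of cord compression, so some at-risk men are expected to be treated. Mandatory CPA is a recognisable approach to that risk. Neither overrides the contraindication.
- The synopsis sentence on consistency with the SPC concerns the regimen, not eligibility. It is not a direct contradiction, but it leaves the departure undisclosed.

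**Conclusion.** The concern holds. As written, the eligibility criteria admit men with known spinal metastases whom the Investigator judges not to be at serious flare risk under CPA, and both attached SPCs contraindicate the drug in those men. The protocol gives no reason for the difference.

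The gap is limited to that group, and its size cannot be derived from the documents. Mandatory CPA and the discretionary exclusions lower the risk. The primary endpoint, the sample size calculation and the analysis are not affected. The text comparison needs no numerical assumption; how often such a man would actually be dosed depends on Investigators' practice and is unknown. The point should be fixed because the possible harm is serious and the correction is small.

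**What to change.** In exclusion 9, in both the synopsis and 4.1.2, add: *or the patient has spinal cord compression or known evidence of spinal metastases (SPC section 4.3)*. Apply it at Screening to the medical history and any existing staging or imaging results. TNM stage alone is not enough, because Appendix 1 codes M1b as bone involvement without the site and allows MX. Inclusion 3 can stay, since metastatic prostate cancer is a licensed indication in both SPCs. If the sponsor intends the departure, the protocol should say so and justify it.

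The cost is an amendment to one clause in two places and some loss of recruitment. Under the illustrative range above, 50 to 72 otherwise eligible men would be needed to enrol 50, and fewer than the upper figure if exclusions 4, 9 and 10 already remove some of them. The clause will not catch undocumented spinal disease, because Screening lists no imaging.

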4.2 Patient Withdrawal Criteria

If one or more of the following occurs, the patient will be withdrawn from the study:

- Patient decision to withdraw from the trial.
- Initiation of any oestrogen, any LHRHa (other than the Decapeptyl SR prescribed for this study) or any antiandrogen (other than the cyproterone acetate two week treatment as described in this protocol).
- Unacceptable safety or tolerability as determined by the Investigator.
- Concurrent, non-cancer related reason, which prevents regular follow up of the patient.
- General or specific changes in the patient's condition, which, in the Investigator's judgement, requires medical intervention and prohibits the patient from compliance with the protocol procedures.

If a patient discontinues from the study prematurely (i.e. prior to completion of the protocol), the primary reason for discontinuation will be determined and recorded. In all cases the Investigator will ensure that the patient receives medical follow-up as necessary.

Patients who withdraw from the study will not be replaced. Under no circumstances will patients be enrolled more than once.

5. STUDY TREATMENT

5.1 Study Medication

Decapeptyl SR 11.25 mg (triptorelin acetate) is presented as a powder for suspension for injection in a sustained release formulation. Each 4 ml glass vial contains 15 mg of Triptorelin acetate plus excipients. The overage is to ensure that a dose of 11.25 mg is administered to the patient. Also supplied is a 3 ml glass ampoule containing 2 ml of mannitol solution 0.8% for injection, which is the suspension vehicle for Decapeptyl SR.

Decapeptyl SR 3mg (triptorelin acetate) is presented as a powder for suspension for injection in a sustained release formulation. Each glass vial contains 4.2mg of Triptorelin acetate plus excipients. The overage is to ensure that a dose of 3 mg is administered to the patient. Also supplied is a 3 ml glass ampoule containing 2 ml of mannitol solution 0.8% for injection. The suspension for injection must be reconstituted following the aseptic technique and using the provided ampoule of mannitol solution 0.8% for injection.

The suspension vehicle should be drawn into the syringe provided using the pink needle and transferred to the vial containing the powder for injection. The vial should be gently shaken and the mixture then drawn back into the syringe without inverting the vial. The needle should then be changed before administering the injection.

Decapeptyl SR should be reconstituted immediately prior to injection.

5.2 Supply of Study Medication

Commercially available supplies of medication will be used for this clinical Study. It is the responsibility of the sponsor to ensure study treatment is relabelled to comply with Annex 13 of the Rules Governing Medicinal Products in the European Union.

5.3 Study Treatment Administration

Study medication will be reconstituted as described above.

Decapeptyl SR 3mg and 11.25mg should be administered by sub-cutaneous injection into the anterior abdominal wall.

5.4 Study Treatment Labelling

The core label texts for all packaging units will comply with the requirements of Annexe 13 of the Rules Governing Medicinal Products in the European Union, and the national laws in force in the UK.

A description of the core text of the IMP labels is displayed below:

- Sponsor name
- Study Number
- Pharmaceutical dosage form
- Route of administration
- Quantity of dose units
- Batch number
- For clinical trial use only'
- 'Keep out of reach of children'

- Name, address and telephone number of the Sponsor, or Investigator (the main contact for information on the product and clinical trial)
- Storage conditions
- Expiry date

5.5 Study Treatment Storage and Accountability

The product should not be stored above 25°C. It should be kept in the container in the outer carton.

Study medication will be stored and dispensed by the trial site's pharmacy department in accordance with Good Clinical Practice and Good Manufacturing practice.

Records will be maintained of the accountability of all study treatments and all used and unused supplies must be retained for verification and drug accountability.

5.6 Compliance

Compliance will be monitored by recording scheduled and actual injection dates and other relevant information on a treatment administration record. All used and unused medication vials and packaging (excluding sharps) will be retained by the Investigator or designee in order to verify compliance.

5.7 Concomitant Medications

All concomitant medications taken during the study will be recorded in the patients CRF. The use of dietary and herbal supplements during the study is not prohibited. All such supplements will be recorded in the concomitant medications page of the patients CRF.

The following concomitant medications are not allowed during the patient's study participation:

- Any medications which raise prolactin levels.
- Any LHRHa other than the Decapeptyl SR prescribed for this study.
- Any other oestrogens or androgens.
- Any anti-androgen from the end of second week after the study Baseline visit.

Changes in concomitant medications taken during the study will be documented.

6. STUDY EVALUATIONS

6.1 Clinical Laboratory Tests

Clinical laboratory tests will be performed by the UHB Pathology Department, [name]. Details of the methodology and reference ranges will be kept in the Trial Site File. Laboratory test results will be recorded on the laboratory results pages of the CRF. All clinically relevant abnormal laboratory tests occurring during the study will be repeated at appropriate intervals until they return to Baseline or to a level deemed acceptable by the Investigator or until the abnormality is explained by an appropriate diagnosis. The total blood during the whole course of the study, taken for serology, biochemistry, haematology, testosterone and PSA will not exceed 75 mL per patient

Blood samples for clinical laboratory tests will be taken at the specified study visits and will consist of the following

Haematology: approx 5mL blood will be collected into a potassium Ethylenediamine Tetra-acetic Acid (EDTA) anticoagulant tube. Parameters to be assessed will include:

- Haemoglobin
- Haematocrit
- Mean cell volume (MCV)
- Mean cell haemoglobin (MCH),
- Mean cell haemoglobin concentration (MCHC)
- White blood cell (WBC) count with differential
- Platelet count.

Biochemistry: approx 5mL blood will be collected into an SST or PST tube. Parameters to be assessed will include:

- Creatinine
- Urea
- Sodium
- Potassium
- Bilirubin
- Alkaline phosphatase (ALP)
- Alanine aminotransferase (ALT)
- Total protein
- Albumin
- Globulin
- Calcium
- Lactate dehydrogenase (LDH)
- Gamma-glutamyl transferase (GGT)
- Total cholesterol
- Triglycerides

Urine analysis (fresh urine): A dipstick analysis of pH, protein, ketones, glucose, bilirubin, blood, urobilinogen and specific gravity will be performed. Further testing (e.g., microscopy and culture) will be carried out at local laboratory at the discretion of the Investigator. Should any clinically significant finding such as infection be noticed, this should be recorded as an Adverse Event and any treatment should be recorded on the CRF concomitant medications page.

